## 12. MTD ESTIMATION AND DLT ANALYSES

In the dose escalation part,  $(x_d, n_d)$  will be observed for  $d=1, \dots, K$ , where  $d$  represents dose levels and  $K$  represents the total number of dose levels. Assuming  $n_d$  subjects have been treated at dose  $d$ , and  $x_d$  of them experienced DLTs, let  $x_d|p_d \sim \text{Bin}(n_d, p_d)$  and  $p_d \sim \text{Beta}(0.005, 0.005)$ . The posterior mean toxicity probability at dose  $d$  is estimated as,

$$\hat{p}_d = \frac{x_d + 0.005}{n_d + 0.01}$$

Isotonic regression will then be applied to the posterior mean DLT rates. Let  $\tilde{p}_d$  represent the isotonic-transformed posterior means for all the doses. The MTD will be the dose that satisfies  $\tilde{p}_d \leq 0.35$  and is closest to the target rate of 0.30. If multiple such doses satisfy the criteria, MTD will be the highest dose level that is  $\tilde{p}_d \leq 0.30$ . If no such doses, MTD will be the lowest dose that is  $\tilde{p}_d > 0.30$ .  $\tilde{p}_d$  is estimated using Pool-Adjacent-Violators Algorithm (PAVA), a solution to isotonic regression.

DLTs will be listed and summarized by MedDRA system organ class and preferred term. The DLT analysis set will be used for summaries.

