- Drug-induced liver injury (Hy's law), including all of the following: greater than $3 \times$ ULN elevation in aspartate aminotransferase (AST) and/or alanine aminotransferase (ALT), total bilirubin $>2 \times$ ULN in the absence of findings of cholestasis (ie, absence of alkaline phosphatase elevation to $>2 \times$ ULN) AND no other etiology to explain the combination of increased ALT/AST and total bilirubin.
- FBS >200 mg/dL on 2 consecutive measurements, at least 24 hours apart, over a 7-day period. In the DLT assessment period, subjects who experience FBS >200 mg/dL must have testing repeated within 7 days.

3.2.4. Definition of Maximum Tolerated Dose, Maximum Administered Dose, and Recommended Phase 2 Dose

The estimated MTD is the dose level associated with approximately 30% of DLT-evaluable subjects experiencing a DLT. The target interval for the DLT rate is 25%-35%. Due to the discreteness of the dose levels and in the interest of the safety of subjects, the estimated MTD is the highest tested dose level with a DLT rate $\leq 35\%$ in at least 6-12 DLT-evaluable subjects. In general, the highest dose in Part 1 that provides an acceptable safety profile (MTD or MAD) will also be the highest dose tested in Part 2 unless one or more of the following suggest that an alternate (ie, lower) dose would be preferable:

- Clinically significant anti-tumor effects observed at a lower dose.
- The frequent occurrence of late and relevant AEs that occur after the DLT period.

The MAD is declared without an MTD based on the highest dose level with an observed DLT rate $<25\%$ (the lower bound of the MTD range) and where sufficient safety and efficacy signals have been observed.

The RP2D is the dose chosen for further study based on assessment of a favorable benefit-risk profile across the totality of Phase 1 study results, including both Parts 1 and 2. The RP2D will

take into account late and relevant toxicities that occur after the DLT assessment period in Part 1 and/or the safety/tolerability of multiple cycles of treatment.

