10.5.2. Estimation of MTD

At the end of Part 1, the MTD selection under the i3+3 design follows the same procedure as in the mTPI and mTPI-2 designs ([Liu et al., 2020](#)). The MTD should be the dose that KZR-261's

DLT rate is closest to the prespecified target DLT rate and within the equivalence interval (EI); to select the dose as the estimated MTD with the smallest difference: $|\hat{p}_d^* - p_T|$ among all the doses d for which $n_d > 0$ and $Pr(p_d > p_T | x_d, n_d) < \xi$. Here \hat{p}_d^* is the isotonically transformed posterior mean of p_d , the same as that in the mTPI design (Zhou and Ji, 2020). If two or more doses tie for the smallest difference, perform the following rule. Let p^* denote the transformed posterior mean \hat{p}_d^* of the tied doses.

- If $p^* < p_T$, choose the highest dose among the tied doses.
- If $p^* > p_T$, choose the lowest dose among the tied doses.

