#### Definition of MTD, MAD, and RP2D

The estimated MTD is the dose level associated with approximately 30% of DLT-evaluable subjects experiencing a DLT. The target interval for the DLT rate is 25%-35%. Due to the discreteness of the dose levels and in the interest of the safety of subjects, the estimated MTD is the highest tested dose level with DLT rate  $\leq 35\%$  in at least 6-12 DLT-evaluable subjects. In general, the MTD will equal the RP2D unless one or more of the following suggest that an alternate dose below the MTD would be preferable:

- Clinically significant anti-tumor effect.
- The MTD is not achieved, in which case the MAD may become the RP2D.
- The occurrence of late and relevant AEs that occur after the DLT period.
- Cumulative toxicity of the MTD or MAD, reflecting that the administration of multiple cycles at the MTD or MAD is not feasible.
- AEs observed beyond Cycle 1 that would require setting the RP2D below the MTD level.

The SRC will evaluate the totality of the events and consider whether they could result from a cumulative toxicity or are significant for the determination of the RP2D.

The MAD is declared without an MTD based on a dose level with an observed DLT rate <25% (the lower bound of the MTD range) and where sufficient safety and efficacy signals have been observed.

The RP2D is the dose chosen for further study based on Phase 1 study results. The RP2D will take into account late and relevant toxicities that occur after the DLT period and/or the cumulative tolerance of multiple cycles of treatment. If the MTD or MAD proves to be clinically feasible for long-term administration in a reasonable number of subjects, then this dose usually becomes the RP2D. Further experience with the MTD/MAD may result in a RP2D dose lower than the MTD/MAD (eg, if in the expansion part >25% of subjects require a dose reduction due to toxicity, then the sponsor may convene an SRC to determine if a lower RP2D needs to be determined).

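### SAP 12 selects the MTD with no lower limit and no MTD-not-reached result, so a Part 1 with no DLTs would report its highest tested dose as an MTD, in conflict with the 25% lower bound stated elsewhere in the plan

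*SAP*

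**What the plan says.** SAP 12 takes the Beta(0.005, 0.005) posterior mean at each dose, applies isotonic regression, and chooses the dose whose estimate is at most 0.35 "and is closest to the target rate of 0.30". Two sentences follow. For several qualifying doses: "If multiple such doses satisfy the criteria, MTD will be the highest dose level that is" at or below 0.30. Then: "If no such doses, MTD will be the lowest dose that is" above 0.30. The section has no lower limit, no minimum number of subjects and no outcome in which an MTD is not found.

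Protocol 3.2.4 and SAP 4.1.1 describe the MTD as the dose at which about 30% of evaluable subjects have a DLT, with a target interval of 25% to 35%. Protocol 3.2.4 adds that "the estimated MTD is the highest tested dose level with a DLT rate" of 35% or less in at least 6 to 12 evaluable subjects. It then says: "The MAD is declared without an MTD based on the highest dose level with an observed DLT rate" below 25%, which it calls the bottom of the MTD range, provided safety and efficacy signals suffice. SAP 4.1.1 foresees the other outcome directly: "The MTD is not achieved, in which case the MAD may become the RP2D".

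Protocol 10.5.2 asks for the dose whose "DLT rate is closest to the prespecified target DLT rate and within the equivalence interval (EI"). The formula after that text minimises the distance to 0.30 over tested doses that are not excessively toxic, and has no lower limit.

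SAP 1 gives SAP methods precedence over the protocol's. SAP 19 declares no changes. Both documents list identifying the MTD or MAD as a Part 1 primary endpoint.

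**The concern.** The two labels make different claims. An MTD says that toxicity limits the dose at a DLT rate near 30%. A MAD says that no such limit was found among the doses tested. SAP 12 is the section a programmer will implement for this endpoint, and it can output only the first label when few or no DLTs occur. The definitions in SAP 4.1.1 and Protocol 3.2.4 point to the second label for the same data, and nothing says which prevails. What is at stake is a primary endpoint reported as a toxicity finding that the data do not contain.

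**Working it through.** **Inputs.** Target 0.30, interval [0.25, 0.35] and cohort size 2 to 4 (SAP 4.1.1). Nine dose levels (SAP Table 2). About 70 subjects (SAP 5). Estimator (x + 0.005)/(n + 0.01) and selection rule (SAP 12).

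**1. The plan's own table.** The i3+3 rule on x/n and (x − 1)/n, with DU when Pr(p > 0.30) > 0.95, reproduces all 90 cells of Table 1. The uniform prior for DU, and no DU at n = 1, are assumptions. The documents give no MTD-selection probabilities to reproduce.

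**2. No DLTs.** With 3 subjects at each of eight doses and 6 at the top, the raw estimates are 0.005/3.01 = 0.00166 and 0.005/6.01 = 0.00083. Isotonic pooling, weighted by n + 0.01, gives 9 × 0.005 / (8 × 3.01 + 6.01) = 0.045/30.09 = 0.0015 at every dose. All nine tie, all are below 0.30, and the tie rule names the top level as MTD. Four other sample-size patterns also named the top level, with estimates of 0.0012 to 0.0017. How the last sentence of SAP 12 is read makes no difference here.

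**3. The 35% sentence read alone.** With 6 subjects it is met by 0, 1 or 2 DLTs. P(X ≤ 2 | n = 6) is 100%, 99.8%, 98.4%, 74.4% and 34.4% at true rates of 0, 5, 10, 30 and 50%. A top dose with 0/6 therefore meets this sentence and also the MAD limit of under 25%.

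**4. Where a selection below 0.25 can arise.** Isotonic estimates do not decrease with dose. Any higher dose with a larger estimate of at most 0.35 would lie closer to 0.30 and be chosen instead, and ties go to the higher dose. So a selected dose below 0.25 is either the highest tested dose or lies below a tested dose with an estimate above 0.35. There is no third case.

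**5. How often.** Assumptions: i3+3 escalation, cohorts of 3, stop at 12 on a dose or 70 in total, 4,000 trials per row. The true rates are assumed, because the documents give none.

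| True DLT rate over 9 doses | MTD named by SAP 12 | Selected estimate below 0.25 | MTD named if 0.25–0.35 required |
|---|---|---|---|
| 0% | 100% | 100% | 0% |
| 2% | 100% | 99.6% | 0.4% |
| 5% | 100% | 93.2% | 6.8% |
| 10% | 100% | 69.9% | 29.6% |
| rising 1–15% | 100% | 64.4% | 35.6% |
| rising 2–30% | 100% | 33.7% | 66.3% |
| rising 5–60% | 100% | 35.3% | 64.7% |

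The Monte Carlo standard error is at most √(0.25/4000) = 0.8 points. With cohorts of 2 and 4, the last column in the 5% row becomes 5.1% and 10.3%.

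The two cases in step 4 divide very differently by scenario. At a flat 5%, nearly all of the 93% are the highest tested dose. In the 5–60% row, essentially all of the 35% lie below a dose already above 35%.

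A check without simulation: at a true 5% and 12 subjects on the top dose, P(0 DLTs) = 0.95^12 = 54% and P(at most 2 DLTs, so under 25%) = 98%.

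**6. Cost of a 25% bound.** If the top dose truly has a 30% rate, the chance that it is observed below 25% is P(X ≤ 1 | 6) = 0.7^6 + 6(0.3)(0.7^5) = 0.118 + 0.303 = 42%. With 12 subjects it is P(X ≤ 2 | 12) = 0.014 + 0.071 + 0.168 = 25%.

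**The case against.** The best defence is that SAP 12 should not be read alone. SAP 4.1.1 is in the same document, so the precedence clause in SAP 1 does not remove it, and it keeps a MAD route below 25%. Its 35% sentence follows statements that the MTD is near 30% with a 25% to 35% interval, so 0/6 is not clearly an MTD when the paragraph is read whole. The gap is also not purely the SAP's: the selection formula in Protocol 10.5.2 has no lower limit either. All of this is correct. It makes the defect an unreconciled conflict between sections, but it does not tell the analyst which label to print.

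A reader might infer more than the documents support:

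- *That a MAD can never be declared.* This is true of SAP 12 in isolation, not of the plan.
- *That an MTD is named whatever the toxicity data show.* This needs the last sentence of SAP 12 to be a general fallback. Read as the second half of the tie rule, as in Protocol 10.5.2, it leaves an all-toxic trial without an MTD: at a true 60% on every dose, only 6.1% of simulated trials name one.
- *That the wrong label would drive the RP2D.* SAP 4.1.1 gives MTD and MAD the same usual route to the RP2D, with exceptions and committee review.
- *That Table 1 contradicts the MTD definition by escalating at 0/6.* Table 1 governs escalation in progress, whereas the MTD is selected at the end of Part 1.

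**Conclusion.** The concern holds as a reporting defect in a primary endpoint. With no DLTs, SAP 12 labels the highest tested dose the MTD at an estimate near 0.001, against a target of 0.30. That conflicts with the 25% bound in SAP 4.1.1 and Protocol 3.2.4 and with the introductory text of Protocol 10.5.2, while SAP 19 reports no change. At an assumed flat 5% DLT rate, about 93% of simulated trials carry an MTD label on an estimate below 25%. The share depends on the assumed rates: it falls to about a third where true rates reach 30% or more, and there many of the selections lie below a dose already seen to be too toxic. The zero-DLT result rests on no assumption about true rates. The simulated shares rest on the assumed rates, cohorts of 3, the stop at 12 per dose and the pooling weights.

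**What to change.** Reconcile SAP 12, SAP 4.1.1 / Protocol 3.2.4 and Protocol 10.5.2:

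- In SAP 12, carry over the plan's own 25% bound. State that when the highest tested dose is selected with an estimate below 0.25, the result is MTD not reached, and the dose is reported under the existing MAD definition, including its condition on safety and efficacy signals.
- State which label applies when the selected dose is below 25% but a higher tested dose exceeded 35%. The documents do not settle this, and a bare 25% floor would leave about 35% of trials in the assumed 5–60% scenario without an MTD.
- Make the 35% sentence in SAP 4.1.1 and Protocol 3.2.4 consistent with the same bound, so that one dose cannot meet both definitions. Say whether the 25% is compared with the isotonic estimate (SAP 12) or the observed rate (the MAD definition).
- Say whether the last sentence of SAP 12 is a fallback or part of the tie rule.
- If the result differs from the protocol, list it in SAP 19.

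This costs a few sentences and no data. The downside is that some trials whose top dose truly has a rate near 30% will report a MAD by chance (25% with 12 subjects on that dose, 42% with 6, from step 6). Which dose goes forward stays with the Safety Review Committee and the sponsor.

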## 13. EFFICACY ANALYSES

All efficacy analyses will be performed on the Response Evaluable Population.

All efficacy data will be listed and summarized with descriptive statistics.

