7.2.10. Response Assessments

Assessments of response and progression will occur in accordance with RECIST v1.1 ([Eisenhauer et al., 2009](#)) at timepoints shown in the Schedule of Events ([Appendix A](#) and [Appendix B](#)). Subjects with mCRPC will be assessed per PCWG3 guidelines ([Scher et al., 2016](#)).

All subjects must have contrast-enhanced imaging studies of chest, abdomen, and pelvis as well as other areas of suspected disease within 28 days prior to their first dose of study treatment. The preferred imaging modality is contrast-enhanced computed tomography (CT). In subjects for whom IV contrast for CT is contraindicated, perform contrast-enhanced magnetic resonance imaging (MRI) scanning of the aforementioned anatomic regions with non-contrast enhanced CT of the chest. Subjects known to have fluorodeoxyglucose (FDG)-avid tumors are required to undergo positron emission tomography (PET) scanning along with the CT scan at Screening. Subjects whose tumors demonstrate FDG update at Screening should undergo follow-up PET scanning post-Cycle 6, post-Cycle 12, and every 6 cycles thereafter (see below). Subjects with skin, subcutaneous or lymph node metastases may also have evaluations of measurable lesions (including measurements, with a ruler or calipers) by means of physical examination.

Subjects with mCRPC must have a baseline PSA and bone scan in addition to the aforementioned imaging studies. (Note: A rising PSA as the sole indicator of disease activity will not lead to a determination of disease progression.) On-treatment bone scans will be performed at the same time points as CT/MRI scans. As a rule, the same imaging modality (ie, CT or MRI or combined CT/PET scans) should be used for all scheduled tumor assessments and measurements.

Imaging studies should be repeated prior to Cycle 3 (ie, end of Cycle 2) and every 2 cycles thereafter (ie, end of Cycles 4, 6, 8, etc). There is a 7-day window for imaging procedures to allow time for availability of results prior to the next cycle. If an imaging procedure must be scheduled to occur outside the 7-day window, this should be discussed with the Medical Monitor for approval prior to the procedure.

Response assessments, including imaging studies, are to be performed at the EOT visit, if PD has not already been established and the last response assessment was conducted >4 weeks prior to EOT.

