Subjects who discontinue study treatment for reasons other than PD will be contacted by telephone approximately every 90 days for 12 months after last study treatment for evidence of PD, collection of information about subsequent anti-tumor therapy, and assessment of survival status. Subjects who discontinue study treatment for PD will be contacted by telephone approximately every 90 days for 12 months after last study treatment for assessment of survival status.

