10.2. Analysis Populations

Three (3) analysis populations are planned for the study as follows:

- The Safety Population consists of all subjects who receive at least 1 dose of study treatment (KZR-261) and will be used for the safety analyses.
- The Response Evaluable Population is defined as all subjects who receive at least 1 dose of study treatment (KZR-261) and who have a baseline and at least 1 post-baseline anti-tumor response assessment using RECIST v1.1.
- The PK Analysis Population consists of all subjects who receive at least 1 dose of KZR-261 and who have at least one post-dose PK sample with measurable concentration of KZR-261. Any protocol deviations affecting PK analyses may result in exclusion from summaries for individual time point concentrations, complete profiles, and/or PK parameters. These exclusions will be reviewed before database lock and confirmed with the Sponsor before implementation.

Unless otherwise specified, all data will be summarized by dose level and overall for Part 1 (Dose Escalation), tumor-specific cohort for Part 2A (Dose Expansion), and dose and tumor-specific cohort for Part 2B (Dose Optimization).

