10.5.8. Handling of Missing Data

Subjects discontinue study treatment and/or the study for any reason will be included in all analyses regardless of the duration of treatment. There will be no imputation for missing data, unless otherwise specified in the Statistical Analysis Plan.

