### **6.2. Response Evaluable Population**

The Response Evaluable Population is defined as all subjects who receive at least 1 dose of study treatment (KZR-261) and who have a baseline and at least 1 post-baseline anti-tumor response assessment using RECIST v1.1 or PCWG3 in the case of mCRPC. The Response Evaluable Population will be used for the efficacy analyses.

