### **13.2.3. Progression-Free Survival (PFS)**

PFS is defined as the date of initiation of KZR-261 until the date of documented PD or death from any cause, whichever occurs first.

$$PFS \text{ (weeks)} = \frac{([Date \text{ of } PD \text{ or } Death - Date \text{ of } First \text{ Dose} \text{ of } KZR - 261] + 1)}{7}$$

For subjects who have neither progressed nor died, PFS will be censored at the date of the last evaluable disease assessment. The median PFS will be estimated using Kaplan-Meier methods and summarized.

Progression-Free Survival at 4 months (PFS4) is defined as the percentage of subjects alive and progression-free at 4 months (ie, 17 weeks) after the initiation of study treatment. The PFS4 responders will be summarized using frequencies and percentages. Similar to analysis of ORR, two-sided 90% CIs for PFS4 responders using the Clopper-Pearson approach will be calculated.

Progression-Free Survival at 6 months (PFS6) is defined as the percentage of subjects alive and progression-free at 6 months (ie, 26 weeks) after the initiation of study treatment. The PFS6 responders will be summarized using frequencies and percentages. Similar to analysis of ORR, two-sided 90% CIs for PFS6 responders using the Clopper-Pearson approach will be calculated.

Separate Kaplan-Meier plots for subjects enrolled to Parts 1, 2A, and 2B will be provided.

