### **13.2.4. Overall Survival (OS)**

OS is defined as the date of first dose of KZR-261 until the date of death from any cause.

$$OS \text{ (weeks)} = \frac{([Date \text{ of } Death - Date \text{ of } First \text{ Dose} \text{ of } KZR - 261] + 1)}{7}$$

For subjects who have not died, OS will be censored at the date the subject is last known to be alive or the date of last contact, whichever is later. The median OS will be estimated using Kaplan-Meier methods.

Separate Kaplan-Meier plots for subjects enrolled to Parts 1, 2A, and 2B will be provided.

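### Limiting all efficacy analyses, including PFS and OS, to subjects with a post-baseline response assessment drops treated subjects who die unassessed and biases the results upward

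*SAP*

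**What the plan says.** SAP Section 13 opens with the rule "All efficacy analyses will be performed on the Response Evaluable Population", and SAP Section 6.2 repeats it: "The Response Evaluable Population will be used for the efficacy analyses". Sections 13.2.1 and 13.2.3 to 13.2.5 name no other set for ORR, PFS, PFS4, PFS6, OS or CBR.

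The population is limited to dosed subjects "who have a baseline and at least 1 post-baseline anti-tumor response assessment using RECIST v1.1" (Protocol Section 10.2). SAP Section 6.2 adds PCWG3 for mCRPC.

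The time-to-event endpoints are defined without reference to any assessment. PFS runs from first dose "until the date of documented PD or death from any cause, whichever occurs first" (SAP Section 13.2.3). For survival, "OS is defined as the date of first dose of KZR-261 until the date of death from any cause" (SAP Section 13.2.4).

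The protocol points the other way. Under Section 10.5.8, subjects who discontinue treatment or the study "for any reason will be included in all analyses regardless of the duration of treatment". Protocol Table 12 lists the expansion and optimization cohorts as the efficacy analysis sets. Protocol Section 10.2 defines the Response Evaluable Population but assigns it no analysis. SAP Section 1 says the SAP's methods override the protocol's, and SAP Section 19 reports no changes.

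**The concern.** For PFS and OS, the rule makes surviving to an assessment a condition of entry. The subjects removed include those with the earliest deaths, so the curves start from a selected group and lie too high. OS needs no scan at all. Subjects who stop for progression "will be contacted by telephone approximately every 90 days for 12 months after last study treatment for assessment of survival status" (Protocol Section 7.2.10), and those who stop for other reasons are also followed for survival. Known deaths of unassessed subjects would be collected and then not used for OS.

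For ORR and CBR, an unassessed subject cannot be in the numerator, so removing that subject from the denominator can only raise the rate.

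The reported figures would describe subjects who reached an assessment, not subjects treated. Although efficacy is a secondary objective, CBR decides whether a Part 2A cohort continues, and the RP2D rests on benefit-risk across all Phase 1 results.

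**Working it through.** **Inputs from the documents.** First scheduled imaging is at the end of Cycle 2, about week 8 (Protocol Section 7.2.10). Part 2A stops a cohort with 1 or fewer of 15 subjects with benefit and otherwise continues to 35 (SAP Section 5). The share of treated subjects never assessed, q, is not given, so a range is assumed.

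**Reproducing SAP Table 3.** With X1 ~ Bin(15, p), stopping if X1 ≤ 1, then 20 more subjects:
- P(futility) = P(X1 ≤ 1). At p = 0.10 this is 54.9% (table: 55%).
- P(at least r of 35) = Σ over x = 2..15 of P(X1 = x) · P(Bin(20, p) ≥ r − x). At p = 0.15 and r = 6, 7, 9 this gives 38.6%, 24.8% and 6.7% (table: 39%, 25%, 7%).

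The table is thus a two-stage binomial with every one of the 15 and 35 subjects in the denominator.

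**Response rates.** Inflation is 1/(1 − q). For example, 7 of 35 treated is 20.0% (90% Clopper-Pearson CI 9.8 to 34.3). With 7 unassessed subjects removed it is 7/28 = 25.0% (12.4 to 41.9).

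**Final Part 2A analysis, true CBR 15%.** Let U be the number unassessed among subjects without benefit, with probability q per treated subject. The quantity is P(X/(35 − U) ≥ 0.25 and not stopped at interim).

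**Interim, all-treated CBR p = 0.10.** Three readings:
- Unassessed subjects stay among the 15: 54.9% stop, as planned.
- They are replaced by evaluable subjects: P(Bin(15, p/(1 − q)) ≤ 1).
- The SAP's gloss of a rate below 7% is applied to assessed subjects only. Then 1/15 = 6.7% stops but 1/14 = 7.1% does not, so P(stop) = (1 − p)^15 + 15p(1 − p − q)^14.

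| q | Inflation of ORR, CBR | P(observed CBR ≥ 25%) at true 15% | P(stop), replaced | P(stop), rate below 7% |
|---|---|---|---|---|
| 0 | 1.00 | 6.7% | 54.9% | 54.9% |
| 5% | 1.05 | 8.2% | 52.1% | 36.0% |
| 10% | 1.11 | 11.6% | 49.1% | 27.2% |
| 20% | 1.25 | 19.9% | 42.4% | 21.6% |
| 30% | 1.43 | 31.0% | 34.7% | 20.7% |

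**PFS4 and PFS6.** If a share d of treated subjects die unassessed, the reported value at any later time is S(t)/(1 − d). A true 30% becomes 33.3% at d = 10% and 37.5% at d = 20%.

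**OS.** Assume exponential survival with a median of 26 weeks. Deaths before week 8: 1 − 0.5^(8/26) = 19.2%. If a fraction f of these are dropped, the reported median is 26 · log2(1/[0.5(1 − 0.192f)]): 34.0 weeks for f = 1 (the upper bound), 29.8 for f = 0.5 and 27.8 for f = 0.25.

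**The case against.** Several points can be made for the plan.

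- **The NE rule.** SAP Section 13.2 gives a best response of NE to a subject who leaves before any assessment and is lost to follow-up, and Section 13.2.1 tabulates NE. This suggests that never-assessed subjects may have been meant to count as non-responders. But such subjects cannot be in the population that Sections 6.2 and 13 prescribe, so the rule adds a contradiction and does not resolve one. It says nothing about PFS or OS.
- **Stage 2 wording.** Protocol Section 10.6 refers to 20 further subjects evaluable for CBR. Read literally (15 enrolled, then 20 evaluable, at least 9 of 35), the 12/20/31% figures shrink to 9/13/18%. The bias is smaller but has the same direction, and the corresponding SAP text omits the evaluability condition.
- **The interim rule is a count.** This stands. The count is unaffected if unassessed subjects remain among the 15, and no text provides for replacement in Part 2A. The lower stopping probabilities apply only if the denominator is read differently.
- **Protocol 10.5.8 may mean within the relevant population.** This is possible, but Table 12 also names whole cohorts.
- **Few subjects may be unassessed.** Eligibility requires ECOG 0 or 1 and excludes illness likely to prevent the first response assessment. EOT imaging is required "if PD has not already been established and the last response assessment was conducted >4 weeks prior to EOT", which captures many living early leavers. It cannot capture a subject who dies before EOT.
- **Subjects who leave alive.** Unassessed subjects who leave alive would add almost nothing to Kaplan-Meier PFS, and removing them could move OS either way. The upward direction for PFS and OS therefore comes from deaths.
- **Efficacy is secondary and descriptive.** This is true, but a descriptive estimate should still follow its own definition.

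**Conclusion.** The concern holds. As written, the SAP deletes events that its own PFS and OS definitions count, and it shrinks the ORR and CBR denominators. Both conflict with the protocol, and no change is declared. The upward direction follows from the documents: for ORR and CBR from any unassessed subject, and for PFS, PFS4, PFS6 and OS from subjects who die unassessed. DOR and best percentage change in target lesions are not affected.

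The size rests on an unassessed share that the documents do not give, and with none unassessed there is no bias. Across an assumed 5% to 30%, ORR and CBR are inflated by factors of 1.05 to 1.43, and PFS4 and PFS6 by up to those factors. The OS figures also depend on the assumed exponential 26-week median. The interim rule is at risk only if unassessed subjects are replaced or the 7% gloss is applied to assessed subjects. In the latter case, one unassessed subject is enough to make the count and the rate disagree.

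**What to change.** 1. In SAP Section 13, analyse PFS, PFS4, PFS6 and OS in all treated subjects, using the Safety Population already defined in SAP Section 6.1.
2. Make all treated subjects the main denominator for ORR and CBR. Count no assessment, or NE, as no response and no benefit. Word the NE rule in SAP Section 13.2 to match, so that it covers every subject never assessed.
3. Keep the Response Evaluable Population as a labelled sensitivity analysis. Leave DOR in responders.
4. In SAP Sections 5 and 18, state that the 15 interim subjects are the first 15 treated, and apply the futility rule as a count. The Table 3 footnote already counts the first 15 subjects without an evaluability condition.
5. Amend the last sentence of SAP Section 6.2. State in Protocol Section 10.2 which analyses the Response Evaluable Population serves, so that it agrees with Section 10.5.8. List any remaining difference in SAP Section 19.

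The cost is SAP wording, a short protocol clarification and one additional set of tables. No new data are needed, because survival is already collected. If any treated subjects die or leave unassessed, the main response rates will be lower than under the current rule. Medians will also be lower where subjects die unassessed.
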